6.5 Monitoring for Subject Compliance

Subject compliance will be based on three assessments, namely, the level of completion of patient 7-day voiding diary, attendance at scheduled follow-up visits plus evaluation of the internal memory of the Neurotech Vital Compact device and the itouch Sure Pelvic Floor Exerciser or the Device Record (diary) to check daily use parameters and schedules.

7 Study Treatments

One device will be issued to each randomized subject in a single-blinded manner. The investigator and those administering the 1-hour provocative stress test, evaluating adverse events and reviewing diary data are to remain blinded regarding treatment assignment.

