11.5 Maintenance of Randomisation and Blinding

A randomisation schedule will be provided. The randomisation schedule is in a permuted block-format randomisation, stratified by study site, to ensure that the subject allocation at the sites remains balanced.

The Subject ID number, randomisation date and patient initials will be recorded along with the allocated treatment.

It is not anticipated that there will be any need to unblind (break the randomisation code) of any subject participating in the study because of an adverse event/adverse device effect, however, the information will be available at the site via the unblinded personnel.

One member of the investigational site team will be responsible for patient training and will consequently be unblinded to required treatment instructions for training. A different member of the team will be responsible for all other patient assessments and CRF completion.

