The Unit Indicators indicate which type of information is being displayed by the Intensity/Time Indicator.

hr

min

sec

1234
5678

The Pad Contact Indicator shows the user which electrode(s) is/are in poor contact with either the skin or with the treatment garment (see page 9).

ELECTRODE DETECTION FUNCTION

During a treatment session, the controller continuously monitors its connection with the electrodes and can detect if they are in proper contact with a patient's skin. If the controller detects a poor quality contact, it alerts the user that there is a problem. This can be caused by one of the following:

- An electrode is missing from the garment(s).
- An electrode is not covering its silver stud on the garment(s).
- Poor contact between the electrode(s) and the skin.
- Poor electrode condition (i.e. with damaged and/or dry surface following too many sessions).

If any of these issues are detected, the controller will:

- Highlight the specific electrode(s) at fault. Please note that there may be more than one electrode concerned.
- Stop the stimulation until the problem is fixed.
- Beep repeatedly until the controller is switched off or the problem is fixed.
- The warning symbol (⚠) will flash until the problem is corrected.

CHECKING / FIXING ELECTRODE FAULTS

Stress Treatment Session

If an electrode detection fault occurs during a Stress Treatment Session, the controller will highlight the faulty electrode(s) with the numbers 1 to 8. The numbers 1 to 8 relate to specific electrodes on each garment, so you know which electrode(s) should be checked. The specific electrode numbers are shown in Fig. 3.

If the unit detects a contact fault:

1. The unit will cease stimulation and indicate which electrode(s) have a problem (Fig. 4).
2. Switch off the controller. Disconnect the stress lead connectors from the garment plugs.
3. Carefully remove the garment(s), as described on Page 12 and move or replace the electrode(s) causing the problem. Make sure none of the liners have been left on the electrodes.
4. Then put the garment(s) back on and press the whole surface of each electrode firmly against the skin. Reconnect the stress lead to the garments and begin the treatment again.
5. If the screen still indicates the same electrode(s) as being faulty, you should try another set of electrodes. If this still doesn't fix the problem, you may have a faulty lead or garment and should contact **neurotech®** or your local distributor for advice.

Fig. 3

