4. Unfasten and then slowly and carefully remove the garment from your left leg. First, peel the garment from the front of the leg until it is half detached and then peel the other end from the rear. Then unfasten and slowly remove the garment from your right leg in the same way.

[figure not shown]

5. Lay the garments on a flat surface and replace the covers on the **black side** of the 8 electrodes, then pack everything away until the next session.

Important: You should only fold the garments once in half, which allows the electrodes to remain flat between sessions.

USING THE LANYARD

1. When using the lanyard, attach it to the lanyard clip at the top of the unit (see page 7). Ensure the unit is attached with the screen facing away from your body.
2. The lanyard is equipped with a safety-clip which pops open if there is a sudden, forceful pull on the lanyard. If this happens, align the two halves of the clip and simply push them back together until the oval button clicks into place (Fig. 21). If it does not "click" together, you may have one side of the clip back-to-front. Turn it around and try again.

INFORMATION BUTTON

The Information Button is used to display various information about your current and previous treatment sessions. Each time you press the button a new element of your treatment progress is displayed on screen. This information remains on screen for 3 seconds and will then revert back to the countdown timer unless you press the Information Button again. The information is displayed in the following sequence:

1 Press: Displays your current intensity level (Fig. 22).

Fig. 22

Fig. 23

Fig. 24

[figure not shown]

Fig. 25

[figure not shown]

Fig. 26

[figure not shown]
[figure not shown]

Fig. 27

2 Presses: Displays the maximum intensity reached during any session to date (Up to 90 sessions - Fig. 23)

3 Presses: Displays the average intensity of all sessions completed to date (Up to 90 sessions - Fig. 24)

4 Presses: Displays the total number of sessions completed to date, up to 2000 sessions. This includes partial sessions, where the full 30 minutes were not completed (Fig. 25).

5 Presses: Displays the total amount treatment time completed to date, up to 199 hours and 59 minutes (Fig. 26)

6 Presses: Displays the treatment code for this particular unit. You should check that your unit displays U205. If another code is displayed, you should contact Neurotech or your local distributor for advice (Fig. 27).

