Some product materials can be re-used if you bring them to a recycling point. By re-using some parts or raw materials from used products you make an important contribution to the protection of the environment. Please contact your local authorities if you need more information about collection points in your area.

Waste Electrical and Electronic Equipment can have potentially harmful effects on the environment. Incorrect disposal can cause harmful toxins to build up in the air, water and soil and can be harmful to human.

WARRANTY

Bio-Medical Research Limited (BMR Ltd.) warrants (a) that your Vital Compact controller will be free from defects in material and workmanship for a period of two years from the date of original purchase and (b) that the Vital Compact garments will be free from defects in material and workmanship for a period of six months from the date of original purchase. These warranties do not apply to the batteries supplied with your product and exclude consumables such as the electrodes.

Should your controller or either garment develop a fault within the warranty period, BMR Ltd. will replace or repair it/them free of charge, provided the controller and/or garment:

- have been used for their intended purpose and in the manner described in this instruction manual;
- have not been connected to an unsuitable power source;
- have not been subjected to misuse or neglect;
- have not been modified or repaired by anyone other than an approved **neurotech®** distributor or agent.

This warranty complements existing applicable national guarantee obligations and does not affect a consumers statutory rights.

Assistance:

If you have any problems with your device please contact your study doctor whose contact details are on the Informed Consent form you received at the beginning of the study. For further assistance you may contact:

Expedite Research, LLC
[name]
[name]
Office [name]

These instructions for use were created specifically for study BMR-13-1001 by:
Bio-Medical Research Ltd.,
[name].

Copyright © 2015 Bio-Medical Research Ltd. All rights reserved.
neurotech® and neurotech Vital® are registered trade marks of
Bio-Medical Research Ltd.

For Investigative Purposes Only. For Use in Clinical Trial BMR-13-1001.
NT Vital Compact US Trial IM - V1

QUICK START GUIDE

Vital COMPACT

Before You Start

[figure not shown]
Unpack The Contents

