14.12 Appendix XII. itouch Sure Pelvic Floor Exerciser Instructions for Use

Instructions for Use

itouchsure

PELVIC FLOOR EXERCISER

IMPORTANT: Read this manual carefully before starting to use your itouch sure Pelvic Floor Exerciser. INAPPROPRIATE OR INCORRECT USE COULD BE UNSAFE.

This user manual is provided to you as part of your participation in a clinical study. Please only use the iTouch sure as directed by your study doctor

Caution: U.S. Federal Law restricts this device to sale by or on the order of a licensed healthcare practitioner.

Support

Please call your study doctor if you have any questions.

TABLE OF CONTENTS

CONTENTS OF PACKAGE	3
Before you use itouch sure for the first time	3
CONTRAINDICATIONS, WARNINGS AND PRECAUTIONS	4
ITOUSH SURE INDICATIONS FOR USE	5
TREATING URINARY INCONTINENCE	6
HOW TO SET UP AND USE itouch sure	7
ITOUSH SURE "SMART FEATURES"	9
ITOUSH SURECONTROLS	11
SCREEN DISPLAYS	14
Treatment	16
BATTERY USE	17
ITouch SURE CLEANING AND STORAGE	18
TROUBLESHOOTING	19
PRODUCT SPECIFICATIONS	19
PROGRAM SETTINGS	20

CONTENTS OF PACKAGE

Itouch Sure Control Unit
itouch sure Electrode
Connecting lead wire
Four AA batteries
Instruction booklet
Storage pouch

Before you use itouch sure for the first time

An examination of the vaginal tissue should be completed prior to initial treatment to rule out any contraindications, establish the baseline tissue condition and assess the physiology discussed below. Pelvic floor stimulation may not be successful if the urethra has excessive scarring or if there is significant denervation of the pelvic floor. The neuromuscular structures involved in urine storage must also be at least partially preserved. Patients with intact sacral reflex arcs and some innervation of the pelvic floor may benefit from pelvic floor stimulation.

The itouch sure unit must only be used in accordance with the advice of your treating physician. Be sure to read the instructions included in this booklet to supplement the information provided to you by your physician.

CONTRAINdications, WARNINGS AND PRECAUTIONS

Contraindications

Should not be used if you have any of the following conditions:

If you have a heart pacemaker or a rhythm problem

If you are pregnant or trying to become pregnant

If you have been diagnosed or treated for cervical, or any pelvic, cancer

If you have, or have had epilepsy

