Change your body position; or

Add lubrication to the itouch sure Probe so that it can make a better contact with the vaginal tissue.

If you have taken the above steps above and the alarm still shows, please refer to Troubleshooting section for further information.

Treatment

Please follow the instructions for use given to you by your study physician. The initial electrode fitting and the treatment session should be done under medical supervision by study staff.

Set the strength level to that prescribed by your study doctor. If you experience discomfort reset the intensity down one step. Don't "overdo" it early on. As long as you can feel the contractions, itouch sure is working properly. You can build up slowly over a number of sessions.

Your muscles may be sore the next day- the same reaction you would get with any new exercise - and you may need to stop using your itouch sure for a day or two until the soreness goes away, and then start again using a lower strength and shorter treatment time. As the pelvic floor muscles get stronger, you will be able to increase your strength level and time.

[figure not shown]
NOTE: itouch sure cycles between active stimulation and periods of rest. It is normal to feel the stimulation ramp down, stop briefly and then ramp back up again during treatment.

BATTERY USE

Inserting the Batteries

Open the battery cover:

Press down in centre of battery cover and slide the cover downwards in the direction of the raised arrows.

Insert the batteries in the direction shown inside the case. Make sure that the ribbon goes behind the batteries, which makes them easier to remove later. When the batteries are running low, a low battery indicator will show on the screen (battery symbol) and the display will begin to fade. The intensity of your workout, however, will stay the same until the battery runs out and the unit shuts off.

Battery removal and replacement:

When the batteries need to be changed the low battery sign, " BATT", will be displayed on the screen. To remove batteries, pull gently on the ribbon behind them. Remove batteries from your itouch sure unit if the unit is unlikely to be used for a long period.

Battery type:

ONLY use either AA alkaline batteries. . DO NOT mix batteries of different types. Do not try to recharge alkaline batteries. Properly dispose of used batteries, as batteries should not be disposed of with household waste.

Warning:

Keep batteries out of the reach of small children

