PRODUCT SPECIFICATIONS

Maximum Intensity	50V zero to peak.
Setting	0·100 in steps of 0.5
OC cutout	below 160 Ohm.
Constant current	160-470 Ohm 470-2000 Ohm constant voltage.
Channels	Single
Waveform	Asymmetrical rectangular
Max Pulse energy	*Total output limited to 25uC per pulse
Power	2 xAA Alkaline
Battery life	At least 15 hours at 50mA 300uS 50Hz
Adjustable Timer	10, 20, 30 45, 60, 90 min defaults to 20 min
Pause button	"Clock" key when running
Output plug	Fully shielded: touch-proof mini USB
Weight	90 gms without batteries
Dimensions	102 x 53 x 30 mm
Safety Classification	Internal power source.
Type BF	Designed for continuous use. No special moisture protection.
Environmental Operating:	Humidity: 20% - 65% RH
Storage Humidity:	10 to 90% RH Temperature range: 0°C to 55°C
Temperature range	0°C to 35°C

[figure not shown]
The electrical specifications are nominal and subject to variation from the listed values due to normal production tolerances.

PROGRAM SETTINGS

Program	Hz	Pulse Width (μS)	Ramp Up & Down (Sec)	Plateau (Sec)	Off (Sec)	Default Program Duration (Min)
STRESS	50	300	1	5	10	20
URGE	10	200	1	5	10	20
MIXED	20	250	2	5	10	20
TONE	35	250	2	3	6	20

Device Output Parameters and Waveform

The waveform below illustrates a typical output waveform from the iTouch Sure device:

Max Pulse Energy: 23 μ C

Use special precautions regarding EMC according to the information provided below.

Other portable and mobile RF communications equipment can affect performance.
Do not use when adjacent to or stacked with other electrical equipment.

Assistance

If you have any problems with your device please contact your study doctor whose contact details are on the Informed Consent form you received at the beginning of the study. For further assistance you may contact

Expedite Research, LLC [name]
[name]
Office [name]

These instructions for use were created specifically for study BMR 13 1001 by:

Bio-Medical Research Ltd. [name]

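### Both device manuals name the study doctor as first contact for device problems and give no route to unblinded site staff, in conflict with the investigator blind in Protocol section 7

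*Protocol*

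**What the plan says.** **The blind.** The opening paragraph of Protocol section 7 (Study Treatments) reads: "The investigator and those administering the 1-hour provocative stress test, evaluating adverse events and reviewing diary data are to remain blinded regarding treatment assignment". Sections 7.8 and 8.8 let the investigator learn the allocation only where necessary or in an emergency, through unblinded site personnel. Section 11.5 divides the site roles: "One member of the investigational site team will be responsible for patient training and will consequently be unblinded". A different team member does the remaining assessments and completes the CRF.

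**The manuals.** Both state that they were created specifically for this study, so the wording is not inherited commercial labelling.

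- Appendix XI (Vital Compact), Assistance: "If you have any problems with your device please contact your study doctor whose contact details are on the Informed Consent form".
- Appendix XII (itouch Sure), Assistance: "If you have any problems with your device please contact your study doctor".
- Appendix XII, Support: "Please call your study doctor if you have any questions".

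Both Assistance sections list the US study director organisation for further help. Neither manual mentions an unblinded site contact.

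**Other contact routes in the protocol.** Section 4 promises telephone support throughout the study. Section 8.10.4 tells subjects that they may telephone the clinic. Section 8.11.2 describes a Week 1 call covering device use, adverse events and medication changes. None of these says whether a blinded or an unblinded person is on the line.

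**The concern.** The two devices share little vocabulary. One has a vaginal probe and a leads alarm; the other has leg garments, gel pads and a pad-contact alarm. A subject can hardly describe a device problem without naming her device. A written instruction to take such problems to the study doctor therefore tends to carry the allocation to a role that section 7 keeps blinded, and it does so through routine support rather than the exceptional route in 7.8 and 8.8.

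Two kinds of judgement are exposed. Section 8.14 has the investigator rate the relationship of each adverse event to the device, and safety is part of the primary objective (section 3.1). Appendix III has the subject told not to contract her pelvic floor and encouraged to keep pace with a metronome, so the conduct of the primary pad test depends partly on whoever runs it.

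**Working it through.** The point concerns wording, so no arithmetic applies and the plan has no figure to reproduce. The check sets the passages side by side.

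**Step 1. Where does each manual send the subject?**

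| Matter | Vital Compact (Appendix XI) | itouch Sure (Appendix XII) |
|---|---|---|
| Device problem in general | Study doctor first (Assistance) | Study doctor first (Assistance) |
| Any question | No equivalent line | Study doctor (Support) |
| Persisting electrode, lead or garment fault | Manufacturer or distributor (Checking / Fixing Electrode Faults) | No separate route |
| Wrong treatment code | Manufacturer or distributor (Information Button) | Not applicable |
| Unclear data-review instructions | Manufacturer (In-Program Information) | Not applicable |
| Persisting unit error | Manufacturer (Problem Solving Guide) | No separate route |
| Set-up help, unexpected operation | Clinician or manufacturer (Caring for Your Unit) | Study doctor, under the Support line |

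The Vital Compact exceptions are explicit. After a persisting electrode fault, "you may have a faulty lead or garment and should contact" the manufacturer or local distributor. On the treatment code: "If another code is displayed, you should contact Neurotech or your local distributor for advice". So the general line is common to both arms, but only the itouch manual sends all questions to the study doctor. How often calls reach the site could therefore differ by arm.

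**Step 2. Is the study doctor a blinded role?** No section defines the term. Section 7 blinds the investigator, and the study doctor is most naturally read as the investigator. The itouch manual, however, assumes a study doctor who knows the device: "Set the strength level to that prescribed by your study doctor". Either the study doctor is the blinded investigator and the manual conflicts with section 7, or it is someone else and the manual does not say so. Both readings call for reconciliation.

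**Step 3. Does anything divert the call?** Sections 8.8 and 11.5 provide for unblinded personnel who allocate the device and train the subject. Section 8.11.5 gives them the electrode checks and the device data at visits. No section gives them telephone support between visits. The synopsis and sections 2.5 and 7.5 have the blind verified at monitoring visits, which can detect a breach but does not redirect a call.

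**Step 4. What follows if the manual is followed as written?** A call about a probe or a garment is likely to disclose that subject's arm to whoever answers as study doctor. It affects adverse event relatedness if that person is the investigator, and the pad test only if that person also administers it.

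**The case against.** The strongest reply has four parts.

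1. *The recipient of the call is unknown.* The manuals give no site number. They point to the consent form, which is not in the review copy. The clinic line in 8.10.4 and the telephone support in section 4 are compatible with unblinded staff answering. This stands: disclosure is likely, not certain.
2. *The blind is stated more narrowly elsewhere.* The synopsis and sections 2.5 and 7.5 blind the personnel who perform the follow-up assessments, and no section says that the doctor who takes calls runs the stress test. This limits the exposure of the primary endpoint. It does not remove the conflict with section 7, which names the investigator and the adverse event evaluators.
3. *The primary measure is fairly objective.* It is a pad-weight difference on a balance calibrated each assessment day, after a scripted test. This also stands, though coaching leaves some room for influence.
4. *Many Vital Compact faults bypass the site.* This is correct.

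A reader might go further and infer that both manuals send every device question to the study doctor, or that any support call necessarily unblinds the investigator. The Vital Compact exceptions contradict the first, and part 1 above leaves the second unproven. A reader might also want to convert disclosure into a bias in the responder difference and an inflated false non-inferiority rate against the 5% margin. That would need a call rate, the share of calls reaching the pad-test assessor, and the size and direction of the resulting shift. The documents supply none of these, and the direction could go either way.

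**Conclusion.** The concern holds as a conflict of wording with a plausible route to unblinding. Both manuals name the study doctor as first contact for device problems, section 7 keeps the investigator and adverse event evaluators blinded, and no available section sends device calls to the unblinded staff the site already has.

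This rests on one strong but unconfirmed inference: that the study doctor is the blinded investigator. The main exposure is to investigator-judged adverse event relatedness. The coached pad test is exposed only if the same person runs it. No numerical bias can be supported. The change is worth making because it protects a blind that the protocol already requires, at very little cost.

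**What to change.** - In the Assistance sections of Appendices XI and XII and the Support section of Appendix XII, name the site's designated unblinded device contact for set-up, use and malfunction questions.
- In Protocol 8.10.4 and 8.11.2, state that this person handles device-use calls, including the device-use part of the Week 1 call.
- Leave section 7.8 and the route for medical concerns and adverse events to the investigator unchanged. Asking that medical concerns be passed on without naming the device would clash with 8.14, which has the investigator judge device relationship and requires device details for each event.
- If the sponsor intends the study doctor to be someone other than the blinded investigator, say so in the manuals and in section 7.

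The cost is three contact lines in two sponsor-written manuals and a sentence in each of two protocol sections. The downside is that the existing unblinded staff member takes the calls.
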